### 9.5.1: Primary Outcome

For the primary outcome, (to be explored as described in Specific Aim 3, once feasibility is examined in Specific Aim 2), a score of 70 on the PROMIS Pediatric Depression Scale short form t-score. To assess incident depression, we will use exploratory nonparametric (Kaplan-Meier plots) and semi-parametric analyses (Cox proportional hazards models) to examine the trends in incident depression within and between treatment arms. If too few students reach the target of 70 (2 standard deviations above the population mean), we will explore outcomes using a target of 65 (1.5 standard deviations above the population mean). We had originally planned to use the SMFQ, but the SMFQ was collected only 5 times for those with complete data and the PROMIS Depression score was collected weekly, making it a much more reasonable measure for a time-to-event analysis.

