## 1.2: Secondary Objectives

### Specific Aim 2

To test the feasibility of an exploratory clinical trial involving a mindful self-compassion intervention, the MFY program (treatment group), and a comparison attention-control among 14-17 year old adolescents (participants may turn 18 after enrollment) with subsyndromal depression. Study results will guide the development of an adequately powered clinical trial in terms of recruitment needs and logistics, equivalence of credibility of the two programs, and participants’ willingness to complete assessment instruments, adhere to study protocols, and complete the study.

#### Purpose 2

Study results will guide the development of an adequately powered clinical trial in terms of recruitment needs and logistics; subjects’ acceptance of the treatment and control programs;

equivalence of credibility of the two programs; and subjects' willingness to complete assessment instruments, adhere to study protocols, and complete the study.

### Specific Aim 3

With feasibility being tested in Aim 2, we will explore primary and secondary outcomes and mediators in response to the MFY program in Aim 3, including time to incident depression by the time of the 36-week follow-up (i.e., MDD-major depressive disorder) (primary outcome); resilience, change in depressive symptoms (secondary outcomes); and rumination, negative cognitive style, and shame (potential mediators).

#### Purpose 3

This study intends to analyze, in an exploratory fashion, the following: incident depression (primary outcome); change in depressive symptoms and resilience (secondary outcomes); and rumination, negative cognitive style, and shame (potential mediators).

Measures are collected at baseline, halfway through the 8-week course, after completion of each 8-week program, at 22 weeks post-program, and at 36 weeks post-program. Analyses are conducted to inform the planning of an adequately powered randomized controlled trial.

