### 3. STUDY DESIGN

---

[figure not shown]
In this study, we will refine and feasibility-test our mindful self-compassion program and an attention control program with a focus on adolescents who are experiencing subsyndromal depression. Subsyndromal to mild depression is defined as a score of at least 6 and 10 on the Quick Inventory of Depressive Symptoms (QIDS). The intervention program, called “Making Friends with Yourself” (MFY), implements mindfulness and self-compassion training. The control condition is a healthy lifestyle program for high-school aged adolescents. The control condition was developed by our team as an attention control group for our pilot adolescent mindfulness program and will be adapted for comparison with the MFY intervention. The 8-week programs will be piloted with a total of 80 adolescents. After completion of the 8-week program, the teens will participate in a post-group meeting to give feedback about program contents. Feedback will take place in the form of a focus group. Following the 8-week program, adolescents will be invited to participate in 6 monthly continuation sessions, designed to strengthen understanding of the topics presented in the 8-week course. Measures of depression, resilience, brooding, shame, mindfulness, and self-compassion will be obtained before the 8-week program, halfway through the program, after the 8-week program (intervention phase), and 3 and 36 weeks after program completion (continuation phase). Feedback from program participants will inform modifications and refinement of both programs.

Our primary goal is to examine the feasibility of implementing the program. After feasibility, the primary outcome to be explored will be the occurrence of incident major depressive disorder (MDD) with a secondary outcome to be explored being the trajectory of depressive symptoms over time (measured at baseline, program end and at 3 and 36 weeks post program) using the Short Mood and Feelings Questionnaire (SMFQ) administered to both the adolescent and a parent. Studies indicate high predictive validity in adolescent self-report of depression. The study psychologist will contact parents of teens with incident major depression, captured by the SMFQ at any of the scheduled time-points during the study, for referral to appropriate mental health care.

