**Patient-Reported Outcomes Measurement Information System Pediatric Short Form (PROMIS Pediatric Short Form)**: The PROMIS Pediatric Short Form is a short 12-item survey designed to screen for depression. The PROMIS Pediatric Short Form will be used as a safety measure once participants are in the 8-week course to assess any changes in depressive symptoms. See [7. Safety Assessments](#) for more details about the PROMIS Pediatric Short Form being used as a safety measure for the study. A T score of 70 on the PROMIS depression measure will generate a referral to the study psychologist.

**Demographics:** The study is limited to adolescents experiencing subsyndromal depression. The demographic survey, administered at baseline, will collect data about each teen’s age, gender, race/ethnicity, years of education, and parental educational attainment.

**Qualitative measures:** We will collect two types of formal qualitative data: 1) Evaluation (focus) groups following each 8-week set of classes at the end of the last class; 2) Transcriptions of audio-recorded classes. The focus groups will address the following topics related to the teens’ experience with the programs, including:

- 1) Most memorable aspects of program (e.g. most favorite and least favorite aspects);
- 2) Whether they would recommend it to a friend;
- 3) Usefulness, challenges and recommended changes including in-class and out-of-class assignments;
- 4) Usefulness of the program for management of stress, mood, and well-being in daily life;
- 5) Tools that might help them maintain practices; and
- 6) Unfulfilled expectations of the program.

Each focus group will be audio-recorded and transcribed.

Table 2. Study measures		
MEASURE	CONSTRUCT	TIMING
Inclusion/Exclusion Criteria		
QIDS-SR	Depression screening	Pre-screening
Diagnostic Interview Schedule for Children (DISC-IV)	Screening for serious psychopathology	Screening visit
Primary Outcomes		
PROMIS Pediatric Depression Short Form v1.1	Incident major depression	Weekly from the beginning of the intervention
Secondary Outcomes		
Short Mood and Feelings Questionnaire (SMFQ-C)	Depression scores change	Visit 2, Visit 6, Visit 10, Visit 13, Visit 16
Brief Resiliency Scale (BRS)	Resiliency	Visit 2, Visit 6, Visit 10, Visit 13, Visit 16
Exploratory Mediating Measures		
Adolescent Cognitive Style Questionnaire (ASCSQ)	Cognitive Style	Visit 2, Visit 6, Visit 10, Visit 13, Visit 16

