### 9.4.2: Individual stopping rules

If a participant scores above 12 on the combined parent and child SMFQ at any point in the study, s/he will be referred to the study psychologist ([name]) within 24 hours. The study psychologist will then contact the parent of the teen (within 24 hours) to inform the parent of the depression status of the teen. [name] will make an evaluation to determine if s/he can continue in the study and will refer the family for appropriate psychological care.

We have added a safety depression screening measure, the PROMIS pediatric depression scale, which will be administered weekly via REDCap. The Assessment Center at NIH provides a scoring algorithm with REDCap software, enabling use of the measure for safety monitoring. The Project Manager or trained designee will monitor these measures weekly and will alert the team (including the Study Psychologist) to sharp increases in depressive symptoms and depressive symptoms meeting criteria for major depression. If the Study Psychologist confirms the development of major depression, the adolescent will be withdrawn from the study and referred for further care.

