**MDD**

I'm now going to ask you some questions about feeling sad and unhappy.

- |   |                               |
|---|-------------------------------|
| 1. In the last year – that is, since [[NAME EVENT]/[NAME CURRENT MONTH] of last year] – was there a time when you often felt sad or depressed?  | 0    2    7    9    [16]      |
| IF YES, A. Was there a time in the last year when you felt sad or depressed for a long time each day?  | 0    2    7    9    [17]      |
| IF NO, GO TO Q 2   |                               |
| B. Would you say that you felt that way for most of the day ?  | 0    2    7    9    [18]      |
| C. Was there a time when you felt sad or depressed almost every day ?  | 0    2    7    9    [19]      |
| IF NO, GO TO Q 2   |                               |
| IF YES, D. In the last year, were there two weeks in a row when you felt sad or depressed almost every day?  | 0 2* 7    9    [20]    |
| IF NO, GO TO Q 2   |                               |
| E. When you were sad or depressed, did you feel better if something good happened or was about to happen to you?  | 0    2    7    9    [21]      |
| F. Now, what about the last four weeks ?
Since [[NAME EVENT]/the beginning of/the middle of/the end of [LAST MONTH]], have you felt sad or depressed?                       | 0    2    7    9    [22]      |
| 2. In the last year – that is, since [NAME CURRENT MONTH] of last year – was there a time when nothing was fun for you and you just weren't interested in anything?                   | 0    2    7    9    [23]      |
| IF YES, A. Was there a time when nothing was fun for you almost every day ?   | 0    2    7    9    [24]      |
| IF NO, GO TO Q 3   |                               |
| B. In the last year, were there two weeks in a row when you felt nothing was fun almost every day?  | 0 <del>2</del> 7    9    [25] |
| IF NO, GO TO Q 3   |                               |
| C. Now, what about the last four weeks ?
(Since [[NAME EVENT]/the beginning of/the middle of/the end of [LAST MONTH]]), has there been a time when nothing was fun for you? | 0    2    7    9    [26]      |

0=NO 1=SOMETIMES/SOMEWHAT 2=YES 7, 77=REFUSE TO ANSWER 8, 88=NOT APPLICABLE 9, 99=DON'T KNOW

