**Pediatric Depressive Symptoms - Short Form**

Please respond to each item by marking one box per row.

In the past 7 days.....

	Never	Almost Never	Sometimes	Often	Almost Always
49881 I could not stop feeling sad.	 0	 1	 2	 3	 4
40151 I felt alone.	 0	 1	 2	 3	 4
504171 I felt everything in my life went wrong.	 0	 1	 2	 3	 4
30201 I felt like I couldn't do anything right.	 0	 1	 2	 3	 4
71151 I felt lonely.	 0	 1	 2	 3	 4
20051 I felt sad.	 0	 1	 2	 3	 4
71251 I felt unhappy.	 0	 1	 2	 3	 4
345243 It was hard for me to have fun.	 0	 1	 2	 3	 4

© 2009-2013 PROMIS® Health Organization and PROMIS Cooperative Group

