## 4 CONFIDENTIALITY

### 4.1 Protection of Subject Privacy

Screening will be conducted in a private setting (closed-door office for both telephone contacts and direct contact with the potential participants and participants). All materials generated in the screening process will be stored in locked cabinets under the control of the PI. Electronic materials will be encrypted and password-protected under the control of the PI or designated project personnel. If potential subjects do not meet criteria, personal identifiers (name, contact information) generated in the screening process related to that subject will be deleted, but demographic information (age, grade in school, gender, race, ethnicity, city/town, school) will be kept. The screening database will be maintained separately from the study database.

Materials arising out of the research will consist of paper records, audio recordings of the sessions (no participants will be videotaped) and computer files. No biological materials will be collected. All data will be de-identified and given a research number to be used for all analysis. Audio-files will be deleted once transcribed. Written materials will be stored in locked storage cabinets under the control and scrutiny of the PIs. This space is outside of the normal

pattern of human traffic at UNC. Most of the research data for this project includes surveys and testing instruments filled out on-line by the participants and stored electronically.

Electronic data will be stored in an encrypted and password-protected online database (REDCap). Access to written and electronic data will be limited to the PI, the project manager, research assistant, and the Co-Investigator responsible for data management/quality assurance. The Study Psychologist will have access to a single form to file reports of psychological evaluations. All data – audio recordings, hard copy and electronic files– necessary for analysis will be de-identified and the resulting data files assigned a research number specific for each participant for purposes of analysis. A file linking personal identifiers with participant data, will be maintained in REDCap in a separate file from the main data sets with access limited to the PI and study staff with access needs. No participants will be identified in any presentation or publication.

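### A PROMIS T-score of 70 on a 7-day form is counted as incident MDD without confirmation, although the trial's conduct rules treat that score only as a trigger for a psychologist's evaluation

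*Combined protocol and SAP*

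**What the plan says.** The target is a diagnosis. Specific Aim 3 (Section 1.2) names "time to incident depression by the time of the 36-week follow-up (i.e., MDD-major depressive disorder) (primary outcome", and Section 3 says that "the primary outcome to be explored will be the occurrence of incident major depressive disorder (MDD" is meant. The power statement in Section 9.2.1 is also for time to MDD.

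The event is a score. Section 9.5.1 uses "a score of 70 on the PROMIS Pediatric Depression Scale short form t-score", analysed by Kaplan-Meier and Cox, with a fallback to 65 if too few teens reach 70. Table 2 lists PROMIS under incident major depression, timed "Weekly from the beginning of the intervention". The PROMIS form (Appendix B.e) asks about the period "In the past 7 days".

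The entry interview uses a longer period. The DISC-IV depression module asks: "In the last year, were there two weeks in a row when you felt sad or depressed almost every day". The loss-of-interest and irritability questions have the same duration item.

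The conduct rules treat the score as a trigger. Sections 5.1.3 and 7.1 refer a teen with T of 70 to the Study Psychologist, and the Expected Risks section of the Data Safety Monitoring Plan (DSMP) calls for an evaluation at 70 or more. Section 9.4.2 then states: "If the Study Psychologist confirms the development of major depression, the adolescent will be withdrawn from the study and referred for further care". DSMP Section 7.3 repeats this. On records, DSMP Section 4.1 says: "The Study Psychologist will have access to a single form to file reports of psychological evaluations".

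**The concern.** Reaching 70 is the diagnosis for the analysis but only a reason to look for one in the conduct of the trial. A teen who scores 70, is evaluated and is found not to have MDD is not withdrawn on that ground, yet enters the primary analysis as incident depression. One form covering seven days cannot show the two-week duration that the trial's own interview asks about.

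Weekly collection, the stated reason for choosing PROMIS, helps to date an event but also gives a teen without MDD more chances to cross once. What is at stake is the MDD incidence and hazard ratio that Specific Aim 3 is meant to supply for planning a powered trial.

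**Working it through.** **1. The two uses of the score, side by side**

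| Teen's course | Section 9.5.1 and Table 2 | Section 9.4.2 and DSMP 7.3 |
|---|---|---|
| T of 70, MDD confirmed | Event | MDD, withdrawn |
| T of 70, MDD not confirmed | Event | Not MDD, no withdrawal on that ground |

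The second row is the defect. Section 9.5.1 never says that a single score suffices. That follows from the absence of any repeat or confirmation rule, since a time-to-event analysis would then use the first crossing.

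**2. The plan's own figures**

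Section 9.2.1 gives more than 30% untreated incidence and 80% power for a hazard ratio of 0.52 with 80 teens. Neither figure describes weekly score variation, so there is no stated crossing rate to reproduce. The power figure does not reproduce at that incidence:

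- Events needed (Schoenfeld, two-sided 0.05 assumed): 4 × (1.96 + 0.84)² / (ln 0.52)² ≈ 74.
- Events expected with 30% in controls: treated risk 1 − 0.70^0.52 = 16.9%, so 40 × 0.30 + 40 × 0.169 = 18.8, giving about 29% power.

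That shortfall is a separate matter. It is used here only to show how few confirmed events to expect.

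**3. Chance that a teen without MDD is counted**

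Let p be the chance per weekly form of an isolated score of 70 or more, and w the number of forms. With independent weeks, the chance of at least one crossing is 1 − (1 − p)^w. The values of p are assumptions. The documents disagree on w:

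- 9 forms (W0–W8): the Table 2 safety row and the Appendix B.e heading place weekly PROMIS in the 8-week programme.
- About 26 forms: DSMP Expected Risks speaks of weekly monitoring over 6 months.
- 37 forms (W0–W36): Table 3.
- 45 forms: 8 weeks plus the 36 weeks of follow-up in Section 8.4.

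| p per week | 9 forms | 26 forms | 37 forms | 45 forms |
|---|---|---|---|---|
| 0.1% | 0.9% | 2.6% | 3.6% | 4.4% |
| 0.5% | 4.4% | 12.2% | 16.9% | 20.2% |
| 1% | 8.6% | 23.0% | 31.1% | 36.4% |
| 2% | 16.6% | 40.9% | 52.6% | 59.7% |

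For example, 1 − 0.99^37 = 0.311.

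**4. Effect on the hazard ratio if crossings are equally frequent in both arms**

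Cumulative MDD hazard is −ln 0.70 = 0.357 in controls and 0.52 × 0.357 = 0.185 in the treated arm. Isolated crossings add m = −w × ln(1 − p) to each arm. The observed ratio is (0.185 + m) / (0.357 + m).

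| p per week | 9 forms | 37 forms | 45 forms |
|---|---|---|---|
| 0.5% | 0.57 | 0.68 | 0.71 |
| 1% | 0.62 | 0.77 | 0.79 |

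At p = 1% and 37 forms, m = 0.372 and the ratio is 0.557 / 0.729 = 0.77.

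**5. Would two consecutive high scores be enough?**

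With independent weeks and the same p for every teen, a run of two is rare: 0.43% over 45 forms at p = 1%. Real teens differ in level. A simulation of stable scores assumed mean T 55, between-person SD 7, within-person SD 5 and week-to-week correlation 0.5. Over 45 forms, 27.7% ever reached 70 and 15.2% did so twice running (4.1% were already there on the first form). A run rule reduces the problem without removing it.

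**The case against.** The strongest defence is that Aim 3 is exploratory. Section 9.1 sets hypotheses aside, Section 9.6.1 disclaims adequate power, and Section 9.5.1 openly explains the move to PROMIS. DSMP Section 7.3 even puts T of 70 in brackets after the words on symptoms that meet criteria for major depression. This lowers the consequence but does not remove the mismatch. The next sentence of DSMP 7.3 still requires the psychologist to confirm, and Specific Aim 3 says that the results will inform a powered trial.

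A reader might go further than the documents allow in four ways.

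- **That roughly a third of teens without MDD will be miscounted.** This needs both a 1% weekly rate and collection through week 36 or later. The rate is an assumption, and the collection period is contradicted within the documents.
- **That the hazard ratio must move toward 1.** This needs similar crossing rates in both arms. If a programme lowers symptom level, crossings may fall sharply. With within-person SD 5, independent weeks and 36 forms, a true T of 58 gives 1 − (1 − 0.0082)^36 ≈ 26% crossing, and a true T of 55 gives 1 − (1 − 0.00135)^36 ≈ 5%, a ratio of hazards near 0.16. Bias through unequal form completion likewise needs completion to differ by arm, which no document states.
- **That two consecutive scores should become the primary event.** Such a rule would still count teens whom the psychologist found not to have MDD. The second score also follows the study's own response to the first.
- **That a diagnosis for every crossing is already in the database.** DSMP Section 8 keeps psychological evaluations on paper in the psychologist's office and enters an eligibility report. Section 10.2 describes baseline eligibility only. DSMP Expected Risks mentions case report form entries for increasing symptoms, but no document specifies an MDD yes/no for each referral.

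**Conclusion.** The concern holds as a mismatch between label and measurement. The primary outcome calls a T-score of 70 on a 7-day form incident MDD, while the trial's own rules establish MDD only after the psychologist confirms it. Incidence reported as MDD can therefore be too high. The hazard ratio is diluted only if unconfirmed crossings are about equally frequent in both arms.

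The size is conditional. At 1% per week it is about 9% of teens without MDD over 9 forms and 31–36% over 37–45 forms; at 0.5%, about 4% and 17–20%; at 0.1%, about 1% and 4%. The documents do not say which rate or which number of forms applies. The exploratory status of Aim 3 keeps this at a change that should be made, not one on which the trial depends.

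**What to change.** - In Section 9.5.1 and Table 2, label the score-based event as first week with PROMIS T of 70 or more (severe depressive symptoms), not MDD.
- Report time to psychologist-confirmed MDD, dated to the triggering score, as the MDD analysis. Use the evaluation report and the withdrawal reason (Sections 9.4.2 and 9.4.3; DSMP Section 4.1 and Expected Risks). Check first that a yes/no result for each referral can be retrieved.
- Give two consecutive scores of 70 or more as a sensitivity analysis only.
- State that scores of 65–69 under the fallback lie below the T of 70 referral trigger, so those events are not MDD events.
- Reconcile Table 2 (outcome and safety rows), Table 3, Appendix B.e and DSMP Expected Risks on how long weekly PROMIS is collected.

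The cost is wording, one additional analysis and a check of the psychologist's records. The downside is few confirmed events: about 19 of 80 at a 30% control risk and a hazard ratio of 0.52, or 24 at 30% overall, which gives 29–36% power. The MDD analysis will therefore be descriptive.

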### 9.5.2: Secondary Outcomes

For the secondary outcome, assuming feasibility is established, change in the Short Mood and Feelings Questionnaire (child and parent versions) will be examined in a linear regression in each condition, to test for any effect of either program. Then we will examine the change in depression scores through an

ANCOVA model controlling for baseline depression score and cohort to control for group specific effects. Subsequently, an exploratory analysis will examine the trajectory of changes over time by program arm, using graphical representations of outcomes at each time point by subject, cohort, and program arm as well as a longitudinal random effects model.

Hence, a within-group model would include terms for the follow-up depression score, the overall intercept, the cohort effect, the time effect, and a cohort\*time interaction—to allow the trajectory to vary by cohort—as well as random effects for individual subjects and subjects nested within cohorts. Between program arms, we would add terms for the program arm and its interaction with time.

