### Design and Outcomes

Four cohorts of adolescents, each with 20 participants, will be recruited. In each cohort, twenty individuals will be randomized with 10 each in the mindful self-compassion group (Making Friends with Yourself) and the healthy behavior skills group. In addition, each adolescent will be accompanied by a parent (n=80). Adolescents complete brief weekly questionnaires to assess depressive symptoms as well as a longer set of online questionnaires at baseline, weeks 4 and 8 of the intervention, and 3 and 36 weeks post-intervention. Parents complete a questionnaire at baseline, 3 and 36 weeks post-intervention.

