## 7.2 Justification of Sample Size

Our primary goal is to refine our programs based on mindfulness and self-compassion to prevent MDD among adolescents and to establish the feasibility of its implementation as compared with an active attention-control comparator. Data of multiple types (focus group

recordings, questionnaires) will be captured with attention to complete data capture through frequent participant contact.

**Power and sample size.** Untreated, >30% of adolescents are expected to develop incident depression. Power is calculated for time to incident MDD and change in depressive symptoms. With a sample size of 80, we expect to have 80% power to detect a hazard ratio of 0.52 for time to MDD between the groups as well as >80% power to detect a mean difference of 4 (SD 6) in SMFQ-C + SMFQ-P. It is anticipated that we will screen 160 with the QIDS and 120 with the DISC to achieve a sample of 80 eligible teens (with 80 parents). Our target recruitment estimate is 53 females and 27 males-based on research demonstrating that there are twice as many female teens with subsyndromal depression as males. **Note that all enrollment figures refer to teens.** Each will have the involvement of one parent.

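### The exploratory between-arm longitudinal SMFQ model in 9.5.2 lists no baseline SMFQ and leaves the role of Visit 2 open, so its arm differences are less precise than the like-for-like baseline-adjusted ones.

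*Combined protocol and SAP*

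**What the plan says.** Section 9.5.2 of the protocol gives the SMFQ analyses in sequence. A per-condition regression comes first. Next is a between-arm comparison of change by an "ANCOVA model controlling for baseline depression score and cohort to control for group specific effects". Last is an exploratory longitudinal random effects model, for which "a within-group model would include terms for the follow-up depression score, the overall intercept, the cohort effect, the time effect", followed by a cohort-by-time interaction and random effects for subjects. The section then says: "Between program arms, we would add terms for the program arm and its interaction with time". Neither list names the baseline SMFQ. Section 9.6.1 repeats the within-group list, again without baseline; in place of the ANCOVA it names a paired t-test in each condition.

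The plan points two ways on the role of the Visit 2 score. Section 3 treats it as a point on the curve: "the trajectory of depressive symptoms over time (measured at baseline, program end and at 3 and 36 weeks post program". Section 9.5.2 names only the follow-up score. Table 2 labels the SMFQ-C construct "Depression scores change" and schedules it at "Visit 2, Visit 6, Visit 10, Visit 13, Visit 16", that is, one baseline and four follow-ups.

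Section 7.2 of the Data Safety Monitoring Plan (DSMP) claims ">80% power to detect a mean difference of 4 (SD 6) in SMFQ-C + SMFQ-P". No correlation between baseline and follow-up SMFQ is given anywhere.

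**The concern.** Two between-arm analyses of the same outcome, set out one after the other, handle baseline differently. The ANCOVA uses it and the longitudinal model, as listed, does not. Randomisation is stratified by gender only, so the arms can differ at baseline by chance. A model of raw follow-up levels passes part of that gap into the arm difference and also gives up the precision that a correlated baseline score offers.

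If Visit 2 is instead a response with its own free arm effect, the contrast becomes a comparison of change, which is a different estimator with a different loss. An analyst could follow the text and produce either. With complete data and categorical time, the two estimates differ by exactly the baseline gap. Section 1.2 says that the analyses are meant to inform planning of a powered trial, so arm differences by visit should be defined once and estimated as well as the data allow.

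**Working it through.** **Inputs.** There are 40 per arm: the Précis says "In each cohort, twenty individuals will be randomized with 10 each", for four cohorts. The difference of 4 and SD of 6 come from DSMP 7.2. Four SMFQ-C follow-ups come from Table 2. Assumed, because the plan does not state them: two-sided alpha of 0.05, and a correlation rho between any two SMFQ occasions of 0.3, 0.5 or 0.7. Equal variance and correlation across visits (what a random intercept implies) and complete data are also assumed.

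**The plan's own figure.** The standard error (SE) is 6 × sqrt(2/40) = 1.342, and 4/1.342 = 2.98. Power is Φ(2.98 − 1.96) = 84.6% (83.8% with the t distribution). The stated power of more than 80% reproduces.

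**Variances**, in units of SD² and up to the common factor 2/n, for the mean of m follow-ups, with A = (1 + (m − 1)rho)/m:
- follow-up scores only, no baseline: A
- baseline-adjusted: A − rho²
- change from baseline: A + 1 − 2rho

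For m = 4, A is 0.475, 0.625 and 0.775 at rho 0.3, 0.5 and 0.7. Interval-width ratios are square roots of variance ratios, so they do not depend on the SD or on n.

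**Reading A: only follow-up scores are responses.** Ratio = sqrt(A/(A − rho²)).

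| rho | one visit | mean of four |
|---|---|---|
| 0.3 | sqrt(1/0.91) = 1.048 | sqrt(0.475/0.385) = 1.111 |
| 0.5 | sqrt(1/0.75) = 1.155 | sqrt(0.625/0.375) = 1.291 |
| 0.7 | sqrt(1/0.51) = 1.400 | sqrt(0.775/0.285) = 1.649 |

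Generalised least squares with visits at weeks 4, 8, 22 and 36 gives the same ratio of 1.00 for the arm-by-time SE at each rho. The baseline covariate removes only between-subject variance, and arm-by-time is a within-subject contrast.

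**Reading B: Visit 2 is a response with a free arm effect, time categorical.** Ratio = sqrt((A + 1 − 2rho)/(A − rho²)).

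| rho | one visit | mean of four |
|---|---|---|
| 0.3 | sqrt(1.4/0.91) = 1.240 | sqrt(0.875/0.385) = 1.508 |
| 0.5 | sqrt(1/0.75) = 1.155 | sqrt(0.625/0.375) = 1.291 |
| 0.7 | sqrt(0.6/0.51) = 1.085 | sqrt(0.375/0.285) = 1.147 |

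With time as a linear slope, the excess over a model with the arms constrained equal at baseline is 16%, 9% and 4%.

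**On the score scale**, taking SD 6 as the raw-score SD, with 40 per arm and one visit: the half-width is 1.96 × 1.342 = 2.63 unadjusted and 2.63 × sqrt(0.75) = 2.28 adjusted at rho 0.5. By the normal formula, power for a difference of 4 goes from 84.6% to 87.8%, 93.1% and 98.7% at rho 0.3, 0.5 and 0.7.

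**Size of the baseline gap.** By chance alone its 95% range is also ±2.63 points. Relative to the adjusted estimate, a gap g moves the raw contrast by rho × g and the change contrast by −(1 − rho) × g. At rho 0.5 and g = 2.6 that is +1.3 and −1.3 points, against a target of 4.

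**The case against.** The case for leaving the text alone is substantial.

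- **Baseline is already handled where it counts.** Section 9.5.2 contains a baseline-adjusted between-arm ANCOVA and labels the longitudinal model exploratory. Section 9.1 sets hypothesis testing aside, and 9.6.1 disclaims adequate power. This stands and limits the consequence.
- **The trajectory contrast may be sound already.** Section 3 puts baseline on the curve. Arm-by-time is then a difference in change, with any baseline gap absorbed by the arm main effect. This stands as to bias. It does not remove the precision loss under Reading B, and 9.5.2 does not adopt that reading.
- **The magnitude rests on an unknown correlation.** This stands: any single percentage would be an assumption. On both readings, however, the loss at a given visit or average keeps the same direction over the range.
- **The SD and the visit count are unclear.** DSMP 7.2 frames its calculation as change, so SD 6 may be the SD of change. The interval ratios are unaffected, but the power figures are. That SD also belongs to the combined child and parent score, and the parent schedule varies: Section 5.1.2 and Table 3 give three parent follow-ups, Table 2 gives four and the Précis gives two. Under Reading A at rho 0.5, the excess for the average is 26% with three follow-ups and 22% with two, instead of 29%. Those passages need reconciling.

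A reader might go further and infer that the longitudinal model is always weaker than the ANCOVA. The arithmetic does not support that. At rho 0.5 the unadjusted mean of four visits has variance 0.625, against 1 − 0.25 = 0.75 for a single-visit ANCOVA. Under Reading A the order reverses only above rho of about 0.57, where (1 + 3rho)/4 = 1 − rho². The loss is real only when the same visit, or the same average, is compared.

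**Conclusion.** The point holds in a limited form. The listed terms contain no baseline SMFQ, the preceding ANCOVA does adjust for it, and the plan does not settle whether Visit 2 is a response or is left out.

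Under Reading A, arm differences at a visit or averaged over visits carry part of any chance baseline gap. Their intervals are wider than needed by about 5% to 11% at rho 0.3, 15% to 29% at 0.5 and 40% to 65% at 0.7. Under Reading B, the categorical-time change contrast is about 8% to 51% wider than the adjusted one over the same range. These figures rest on the assumed rho, a random-intercept covariance and complete data.

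It would be wrong to infer that every arm contrast in the model carries baseline imbalance. Under Reading A, arm-by-time is unaffected by a baseline covariate. Under Reading B, it is already a change from baseline and does not carry the raw gap. Nor do the documents say that this model supplies the future trial's effect size; Section 1.2 says only that the analyses inform planning. This is a worthwhile improvement to an exploratory analysis and not a flaw in the plan's baseline-adjusted SMFQ comparison.

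**What to change.** In 9.5.2 and 9.6.1, state the role of the Visit 2 SMFQ in the between-arm longitudinal model and choose one of two forms:

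1. Keep the follow-up scores as the response, and add the Visit 2 SMFQ and its interaction with visit as covariates.
2. Keep Visit 2 as a response, with the two arms constrained to a common mean there.

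Take the arm difference at each visit from that model. If a precision gain is quoted, give it as a range over assumed correlations.

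The cost is a few lines of text and one covariate with its interaction, or one constraint. The Visit 2 score is already collected and already used in the ANCOVA, so no new data or visits are needed.
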